4.4 ADJUNCTIVE THERAPY / PROCEDURE

Not applicable.

4.5 ACCEPTABLE CONTRACEPTIVE REGIMEN

Pylera® capsules of bismuth subcitrate potassium, metronidazole and tetracycline hydrochloride given with omeprazole are considered contraindicated for use during pregnancy. Nevertheless, current regulations and guidelines pertaining to pharmaceutical industry require properly documenting and monitoring exposure to any investigational or marketed drugs under clinical research during pregnancy of study female subjects and the partner of study male subjects.

It is expected that women of childbearing potential will have already been appropriately screened by the Investigator as per the “Pregnancy and lactation” section of the Pylera® SmPC and that such individuals who are not pregnant and not nursing will take appropriate measures to prevent pregnancy while using Pylera®.

Women who are pregnant or nursing are excluded from participation in this study.

4.6 DISCONTINUATION CRITERIA

A subject has the right to withdraw from the study at any time for any reason without penalty or prejudice. The Investigator also has the right to withdraw a subject from the study if he/she feels it is in the best interest of the subject or if the subject is uncooperative or noncompliant. Should a subject decide to withdraw, all efforts will be made to complete and report the observations and early withdrawal procedures as thoroughly as possible.

Subjects who withdraw subsequent to the signing consent but before receiving the prescription for Pylera® will be considered “screening failures” and will be replaced to ensure that 200 evaluable subjects complete the study.

Discontinuation may occur because of any one of the following reasons among others:

#	Discontinuation criteria
1	The subject has been included in violation of the inclusion / exclusion criteria

2	The subject chooses to discontinue participation for personal reasons (moving away, no time, etc.)
3	The subject chooses to discontinue, or is discontinued by the Investigator or the sponsor, due to an AE
4	The Investigator or the sponsor discontinues the subject for a significant protocol deviation
5	A newly developed illness, as determined by the physician in charge, that compromises continued participation
6	The subject uses a prohibited medication during the study (as described under Section 4.3.2)
7	In the Investigator or sponsor's judgment, withdrawal from the study would be in the subject's best interest (e.g., an immediate medical or surgical procedure is required that would compromise the subject's continued participation, lack of adequate therapeutic response resulting in intolerable symptoms or unacceptable risk)
8	The subject is uncooperative or does not comply with the protocol requirements (e.g., failure to return for scheduled visits at the enrolling study site, failure to complete study evaluation, etc.)
9	The sponsor terminates the study

For any subject who leaves the study, the Investigator must complete the CRF up to the time of withdrawal, ascertain the reason for discontinuation, and perform the EOS procedures. All reasonable efforts must be made to contact subjects who fail to return for scheduled visits and to encourage them to comply with the procedure. All attempts to contact subjects either by phone, courier, and/or email must be clearly documented. In case of withdrawal of consent, the date of withdrawal and the reason for withdrawing consent if provided by the subject will be collected. No additional data will be collected from the time of withdrawal of consent.

In the case of premature voluntary withdrawal of a subject with the premature stop of treatment with Pylera®, the subject will be excluded from the study and will be monitored separately. For subjects who have halted treatment with Pylera® and have withdrawn due to a neurological AE indicative of bismuth encephalopathy, the subject will be followed up through a separate Pylera® Intensive Monitoring Program.

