
Study Procedures:
	
This is a single-arm, open-label trial in presumed H. pylori-positive subjects and is restricted to centers in France.
 
Following identification of participating general practice and specialist study centers, subjects deemed eligible for study will be identified and may be enrolled. To assess eradication, subjects will complete a diagnostic H. pylori test (breath test, biopsy, or other test at the discretion of the Investigator) following a period of at least 28 days after the end of treatment.
 
Subjects who are treatment-eligible will already have a prescription for Pylera® and a PPI (presumed to be omeprazole) and will have been instructed on dosing as the dosing information contained within the Pylera® SmPC: 3 capsules Pylera® QID taken after meals and following a bedtime snack, and omeprazole capsule BID taken after breakfast and evening meal doses of Pylera®, for 10 days (equivalent to daily doses of 480 mg [as Bi₂O₃ equivalent], tetracycline hydrochloride 1500 mg, metronidazole 1500 mg, and omeprazole 40 mg).
 
Subjects will provide two blood samples for assessment of bismuth concentrations (total bismuth in plasma and whole blood and trimethylbismuth (TMB) in whole blood), with one sample provided prior to start of Pylera® treatment (D0) and one sample provided Day 11 i.e. Day 1 after completion of Pylera® treatment. If accumulation of bismuth is detected (defined as whole blood bismuth concentration exceeding 50 µg/L.), subjects will be contacted to immediately return to the laboratory to draw a third verification sample and will be referred for potential inclusion and follow-up in a separate intensive monitoring program. In case of a neurological AE indicative of bismuth encephalopathy (please refer to Appendix 3 – Central Nervous System Adverse Events of Interest) is present at Day 11 blood samples will be as quickly processed as possible.

	
A diagnostic H. pylori test to assess H. pylori eradication should be repeated on one single occasion at least 28 days post-treatment.

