3.2 SCHEDULING OF VISITS

Patient inclusion in the study will be considered after the decision to treat with Pylera® has been made by the Investigator.

The Inclusion Visit will be initiated following signature of Informed Consent.

Information regarding date of Pylera® prescription, name of prescribed PPI, demographic data, vital signs, height, weight, disease history for *H. pylori* infection (including information pertaining to prior *H. pylori* treatment), co-morbidities, medical and surgical history — will be surveyed, as well as information concerning diagnostic procedures performed to verify *H. pylori* infection.

Upon confirmation of eligibility, subjects will be given instructions for the first blood sample (D0 sample) for bismuth and TMB PK prior to initiating treatment with Pylera®, and an appointment for the second blood sampling.

Upon completion of the 10-day treatment with Pylera®, subjects will proceed to the EOT Visit to provide the second blood sample (D11 sample) for bismuth and TMB PK.

Subjects who demonstrate clinical symptoms indicative of bismuth-related neurological adverse events or bismuth accumulation at the EOT Visit (total bismuth in whole blood > 50 µg/L) will be requested to return to the laboratory immediately to draw a third blood sample for evaluation of bismuth. Subjects having clinical symptoms indicative of bismuth-related neurological adverse events will be referred to the separate Intensive Monitoring Program. If bismuth concentration remains sustained in subjects with no neurological symptoms and subject interview with Investigator confirms that no third-party source of bismuth was consumed outside of the context of this study, the subject will be referred to the separate Intensive Monitoring Program to be evaluated for inclusion.

A diagnostic *H. pylori* test (breath test, biopsy, or other test at the discretion of the Investigator) to assess *H. pylori* eradication should be repeated on one single occasion at least 28 days post-treatment as part of the EOS Visit.

Vital signs, concomitant medications, adverse events (AEs) and the presence of central nervous system (CNS) adverse events of interest as listed in Appendix 3 will be assessed at the EOT and EOS Visits.

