4 STUDY POPULATION

4.1 NUMBER OF SUBJECTS

As per requirement by the regulatory authorities, 200 eligible men and women 18 year of age and older will be recruited into the study.

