4.2 SELECTION CRITERIA

4.2.1 Inclusion Criteria

To be eligible, subjects must meet all of the following criteria:

#	Inclusion Criteria Description
1	Men and women 18 years of age and older who have received a prescription for Pylera® therapy from the Investigator
2	Mental and legal ability to give written Informed Consent and judged by the Investigator to be capable of following the procedures outlined within the protocol

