11 DATA MANAGEMENT AND STATISTICS

11.1 SAMPLE SIZE/POWER CONSIDERATIONS

No sample size and power calculations have been conducted for this study as pharmacokinetic evaluations for two hundred (200) eligible subjects has been requested.

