11.7.1.2 Per Protocol Population

The Per Protocol (PP) population will consist of all subjects who have met the following criteria:

- have provided 1st and 2nd blood samples for plasma and whole blood PK data;
- have completed the study without any major protocol violations or other events considered to have potential impact to the full PK profile.

Major protocol deviations include all significant deviations to the protocol related to the inclusion/exclusion criteria, to the conduct of the trial, to the subject management or assessment of safety data and may include but not limited to the following:

- conduct of any study procedure prior to the signature of the ICF
- major deviation to study procedures
- premature withdrawal from study

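### Section 4.6 replaces only withdrawals before the prescription, so the 200 evaluable completers it promises are not ensured

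*Protocol*

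**What the plan says.** Section 4.6 defines who is replaced: "Subjects who withdraw subsequent to the signing consent but before receiving the prescription for Pylera". These are labelled screening failures and "will be replaced to ensure that 200 evaluable subjects complete the study".

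Inclusion criterion 1 (section 4.2.1) admits "Men and women 18 years of age and older who have received a prescription for Pylera® therapy from the Investigator". The synopsis, under study procedures, agrees: "Subjects who are treatment-eligible will already have a prescription for Pylera® and a PPI". Section 3.2 places inclusion after the treatment decision: "Patient inclusion in the study will be considered after the decision to treat with Pylera® has been made by the Investigator".

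The number is worded in three ways:
- Section 4.1: "200 eligible men and women 18 year of age and older will be recruited into the study".
- Section 11.1, which reports that no sample size calculation was made: "pharmacokinetic evaluations for two hundred (200) eligible subjects has been requested".
- Section 4.6: 200 evaluable subjects who complete.

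The protocol does not define evaluable. The nearest definition is the Per Protocol population in section 11.7.1.2. Its members must "have provided 1st and 2nd blood samples for plasma and whole blood PK data" and must have no major violation, with premature withdrawal named as an example of one.

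**The concern.** A replacement rule secures a target only if it is triggered by the losses that reduce the count. Here the trigger comes before eligibility and the losses come after it. The protocol expects such losses: section 1.2 gives poor compliance and misuse as reasons for the study, section 4.6 lists nine grounds for discontinuation, and section 11.6 names sample loss as a deviation.

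Section 11.1 gives the regulator's request as the only basis for the study's size. If fewer than 200 subjects give both samples, the primary objective is reported on fewer subjects than section 4.6 promises, and the protocol contains no step that would prevent it. An analysis plan written before database lock cannot recover subjects who were never replaced, so the point belongs to the protocol.

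**Working it through.** **Step 1. Who is replaced, and who is lost.**

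| Event | Where | Replacement stated? |
|---|---|---|
| Withdrawal after consent, before the prescription | 4.6 | Yes |
| Withdrawal or discontinuation after the prescription | 4.6 (nine grounds) | No |
| Voluntary withdrawal with early stop of treatment: subject leaves the study | 4.6 | No |
| Early stop of treatment: the listed procedures include no PK draw, and the Day 11 sample is listed only for those who completed treatment | 9.2.1, 9.2.2 | No |
| Missing Day 0 or Day 11 sample, or major deviation | 11.6, 11.7.1.2 | No |

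The first row covers people who do not yet meet criterion 1. Replacing them keeps the number of eligible subjects at 200 but offsets none of the losses in the other rows.

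**Step 2. The protocol's own figure.** There is no sample size formula to reproduce, so the check is on the count. If 200 are recruited and a proportion d is lost after the prescription without replacement:

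expected evaluable = 200 × (1 − d)

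This gives 200 only at d = 0. The protocol states no value of d, so every value below is an assumption.

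| d | Expected evaluable | Enrolment for an expected 200 evaluable, 200/(1 − d), rounded up |
|---|---|---|
| 1% | 198 | 203 |
| 5% | 190 | 211 |
| 10% | 180 | 223 |
| 12.5% | 175 | 229 |
| 15% | 170 | 236 |
| 20% | 160 | 250 |

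With independent losses, the chance that all 200 are evaluable is (1 − d)^200: 0.99^200 = 13% at d = 1%, and 0.98^200 = 1.8% at d = 2%.

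**Step 3. What the lower number means for precision.** The protocol does not name a measure for this, so the following is illustrative. Suppose no subject exceeds 50 µg/L. The exact (Clopper-Pearson) one-sided 95% upper limit for the true proportion is 1 − 0.05^(1/n):
- n = 200: 1 − 0.05^(1/200) = 1.49%
- n = 175: 1 − 0.05^(1/175) = 1.70%
- n = 150: 1 − 0.05^(1/150) = 1.98% (this n corresponds to a 25% loss)

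**The case against.** The strongest reply is that the text does not forbid further replacement and sets no cap on enrolment. Section 11.7 produces the final tables once all 200 subjects have completed, and section 11.2 counts interim accrual in evaluable patients. Both fit a plan of recruiting until 200 complete. On that reading section 4.6 is incomplete but the target may still be met. This stands as far as it goes: a shortfall is not certain. But section 4.1 recruits 200, and no passage states a replacement or an allowance for later losses.

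Several stronger readings are tempting, and the documents do not support them:

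- *The replaced category is empty.* Section 9.1.1 gives an enrolment number on willingness to participate, section 9.1.2 confirms the criteria after consent, and section 3.2 refers to the decision to treat, not to the written prescription. A person could consent and withdraw before the prescription is issued. The category exists; replacing its members simply does not protect the eligible count.
- *The study will miss 200.* The text shows only that 200 is not ensured.
- *A precision target or power is lost.* Section 11.1 reports no calculation and section 11.7 makes the analysis descriptive. Section 11.2 even allows a stop at 100 subjects if variability is low, after consulting the regulator. At n = 100 the limit in step 3 would be 2.95%.
- *The Phase I study gives an evaluable share of 28/32.* Section 1.1 reports 32 enrolled and uses 28 as the denominator for peak results, without explaining the difference. It cannot be carried over as an attrition rate to a study with two draws.

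The difference in terms is also narrower than it looks. The wording of 11.1 can be read as a request for 200 PK evaluations, which agrees with 4.6; it is mainly 4.1 that differs.

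**Conclusion.** The concern holds in this form: the stated rule does not secure the 200 evaluable completers that section 4.6 says it ensures. The conclusion rests on the text of 4.1, 4.2.1, 4.6 and 11.7.1.2 and needs no attrition figure. It takes Per Protocol membership, and in particular both blood samples, as the meaning of evaluable.

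The size is modest and conditional. Under an assumed loss of 5% to 20%, 190 to 160 subjects would be evaluable. A fall from 200 to 175 would move the zero-event upper limit by 1.70 − 1.49 = 0.21 percentage points, and a fall to 150 by 1.98 − 1.49 = 0.49. No test or error rate is affected. What is at stake is a stated number that the protocol does not back, and somewhat wider intervals.

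**What to change.** In 4.1, 4.6 and 11.1, use one term for the target. State 200 as the number enrolled, and beside it the expected number of valid Day 0/Day 11 sample pairs under a stated attrition assumption. Delete the clause in 4.6 that promises 200 evaluable completers. This changes wording only; its one downside is that the stated evaluable number becomes slightly less favourable.

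If the regulator did ask for 200 evaluable subjects, keep that number and change the trigger in 4.6: replace any enrolled subject who does not have a valid Day 0/Day 11 pair. The cost is extra recruitment: 11 more enrolments at an assumed 5% loss, 23 at 10% and 50 at 20% (the enrolment figures in step 2 minus 200), to be fitted into the planned 24-month recruitment period.

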1.2 RATIONALE FOR THE STUDY

As part of the Pylera® MAA, a post-marketing PK program to be conducted in France was requested to observe potential changes in bismuth concentrations arising from real-life use of Pylera® in the general population, including poor compliance, misuse, or the concomitant use of other medications.

The present study is designed to address this request.

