4.3.2 Prohibited Medication

It is expected that subjects will have already been appropriately screened by the Investigator as per information listed in the “Interaction with other medicinal products and other forms of interaction” section of the Pylera® SmPC.

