9.2.1 Subjects who completed treatment with Pylera®

Subjects who have completed the 10-day treatment with Pylera® will return to complete the following procedures as part of the EOT Visit:

- Vital signs measurement (blood pressure, pulse rate)
- Recording Pylera® treatment description and compliance
- Recording of concomitant medications
- Recording of AEs

The presence of CNS adverse events of specific interest as listed in Appendix 3 will be assessed at this visit with the specific form “Pharmacovigilance reporting form-neurological disorders and bismuth” developed for the collection of the adverse events of special interest as part of the Intensive Monitoring Program that will be completed by the Investigator.

Subjects will provide one blood sample as the post-treatment sample (D11 sample) for assessment of plasma and whole blood bismuth concentrations as well as whole blood TMB concentrations as per the procedures outlined in Appendix 2.

Subjects who demonstrate bismuth accumulation in whole blood at the EOT Visit ($> 50 \mu\text{g/L}$) will be requested to return immediately to the laboratory to draw a third blood sample for evaluation of bismuth. If bismuth concentration remains sustained and subject interview with Investigator confirms that no third-party source of bismuth was consumed outside of the context

of this study, the subject will be referred to the separate Intensive Monitoring Program to be evaluated for inclusion.

Subjects will return 28 days after the EOT Visit to complete the EOS Visit. At this visit, subjects will complete:

- Vital signs measurement (blood pressure, pulse rate)
- Recording eradication test
- Recording of concomitant medications
- Recording of AEs

The presence of CNS adverse events of specific interest as listed in Appendix 3 will be assessed at this visit with the specific form “Pharmacovigilance reporting form-neurological disorders and bismuth” developed for the collection of the adverse events of special interest as part of the Intensive Monitoring Program that will be completed by the Investigator.

Subjects who demonstrate a positive diagnostic *H. pylori* test (breath test, biopsy, or other test at the discretion of the Investigator) at End of Study will be documented by the completion of a specific form entitled “Targeted follow-up form – Pylera® eradication therapy failure”. These subjects will be referred to treatment for *H. pylori* infection outside of the context of this study.

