9.2.2 Subjects who prematurely discontinue treatment with Pylera®

For any subject who prematurely discontinues treatment with Pylera®, the Investigator will perform the EOS procedures and will complete appropriate pages of the CRF. A diagnostic *H. pylori* test (breath test, biopsy, or other test) will be conducted at the discretion of the Investigator.

In case of withdrawal of consent, only the date of and the reason for withdrawing consent will be collected on the CRF. Otherwise, the Investigator will make all reasonable effort to complete as much as possible the following at the time of discontinuation.

#	Information to be collected
1	Vital sign measurements (pulse rate, blood pressure measured from the same arm throughout the study)
2	Record of any occurrence of AEs, change in concurrent medical conditions, use of adjunctive therapy/procedure, and intake of concomitant medication
3	Collect safety information via a phone call to the patient 30 ± 5 days after discontinuation (includes AEs, change in concurrent medical conditions, use of adjunctive therapy/procedures, and intake of concomitant medication).

4	A diagnostic H. pylori test (breath test, biopsy, or other test) at the discretion of the Investigator
---	--

All results of evaluation and observations, together with the reason for withdrawal from the study, will be recorded on the CRF.

For any subject who prematurely discontinues treatment with Pylera® due to a neurological AE indicative of bismuth encephalopathy, the subject will be followed up through a separate Pylera® Intensive Monitoring Program.

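### Discontinuation criterion 6 lets a subject be withdrawn for using an interacting medicine, so part of the co-medication exposure the study was asked to observe may be lost

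*Protocol*

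**What the plan says.** Protocol Section 1.2 explains that the study was requested to observe bismuth under real-life use, "including poor compliance, misuse, or the concomitant use of other medications".

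Section 4.6 introduces its list permissively: "Discontinuation may occur because of any one of the following reasons among others". Criterion 6 on that list reads: "The subject uses a prohibited medication during the study (as described under Section 4.3.2". Criterion 4 separately allows withdrawal for a significant protocol deviation.

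Section 4.3.2, to which criterion 6 refers, names no medicine. It says only: "It is expected that subjects will have already been appropriately screened by the Investigator", with reference to the SmPC interaction section.

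For a subject who leaves, Section 4.6 has the Investigator "ascertain the reason for discontinuation, and perform the EOS procedures". Section 11.6 lists use of prohibited medication that could affect safety parameters as a deviation, and says that a subject with a major deviation needs sponsor and IRB approval to stay in the trial. Section 11.7.1.2 limits the Per Protocol population to subjects with both blood samples and no major violation, and counts early withdrawal from the study as a major deviation.

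**The concern.** The study supplies no drug (Section 8), and Section 7.2 says that taking part does not affect care. Leaving the study is therefore not the same as stopping Pylera. A subject withdrawn under criterion 6 may go on taking the prescribed capsules while the measurement of bismuth stops.

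The medicines that can trigger this are those flagged for interaction, which belong to the exposure Section 1.2 says should be observed. What is at stake is whether the study can describe bismuth in these users, and whether the overall result reflects routine use or routine use with some of the co-medicated patients removed. A lost analysis-set membership can be restored later. A sample that was not drawn cannot.

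**Working it through.** The protocol has no figure to reproduce here: Section 11.1 states that no sample size calculation was made, and the 200 subjects come from the regulatory request. The check is a tracing of the text, followed by an illustration on assumed figures.

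**Route 1: withdrawal before Day 11**

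- The leaver gets the EOS procedures (Section 4.6). Section 9.2.1 introduces that visit with "Subjects will return 28 days after the EOT Visit to complete the EOS Visit. At this visit, subjects will complete" and lists vital signs, eradication test, concomitant medications and adverse events, followed by the CNS event assessment. There is no blood sample.
- Section 9.2.2, for subjects who stop Pylera early, begins "Otherwise, the Investigator will make all reasonable effort to complete as much as possible the following at the time of discontinuation". Its list has vital signs, events and medications, a telephone call and an optional *H. pylori* test. There is no blood sample here either.
- The flowchart in Appendix 1 places pharmacokinetic samples at Day 0 and Day 11 only.
- The accumulation value in Section 11.7.7 is the EOT concentration minus the Day 0 concentration. Without the second sample it cannot be calculated.
- Section 4.6 replaces only those who withdraw before receiving the prescription, so these losses are not made up.

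**Route 2: use found at the End of Treatment Visit**

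- Medications are recorded at the Inclusion Visit and next at the End of Treatment Visit. Between them, Section 9.2 provides only for recording adverse events if the patient makes contact. Use that starts during treatment will therefore mostly surface at the visit where the Day 11 sample is planned, and the sample can still be drawn.
- The subject can nevertheless be classed as a major deviation (Section 11.6) or as an early withdrawal (Section 11.7.1.2), and so leave the Per Protocol population. The protocol does not say outright which population the bismuth summary uses, but this is the only one it defines by the paired samples.

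**Illustration 1: what could be said about users if they are kept**

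- Assumed share of users: 5% to 15%. Then 200 × 0.05 = 10 and 200 × 0.15 = 30 subjects.
- With no value above 50 µg/L, the exact one-sided 95% upper limit for the exceedance rate is 1 − 0.05^(1/n).
- n = 10: 1 − 0.05^(1/10) = 25.9%. n = 30: 1 − 0.05^(1/30) = 9.5%.
- If all were withdrawn before Day 11, n = 0 and there is no limit at all.

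**Illustration 2: effect on the overall result, if such medicines raise bismuth**

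- Assumed: 10% users (20 of 200), exceedance 5% in users and 0.5% in the other 180.
- Overall rate with users kept: 0.10 × 5% + 0.90 × 0.5% = 0.95%. With all users lost: 0.5%.
- Chance of at least one value above 50 µg/L with users kept: 1 − 0.95^20 × 0.995^180 = 85.5%. With all users lost: 1 − 0.995^180 = 59.4%.

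Both comparisons set full retention against full loss, so they mark the outer limit of the effect.

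**The case against.** The strongest reply is that the loss will seldom happen. The criterion is permissive, no visit falls between Day 0 and Day 11, and a subject found on Day 5 to be using such a medicine would have to have contacted the Investigator unprompted. This stands. A reader might infer that the Day 11 sample of these subjects is never drawn; the documents support that only for withdrawal before Day 11, and even then only where the discretion is used.

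Second, Section 4.3.2 describes screening against the SmPC and does not say that every medicine listed there is prohibited. That is fair. But criterion 6 then refers to a section that defines nothing, so sites may apply it differently.

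Third, a reader might infer that the primary result is biased toward no accumulation. The SmPC is not part of the documents, and Pylera has three active components, so nothing shows whether the listed interactions raise, lower or leave bismuth unchanged. The statement holds only conditionally.

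Fourth, a reader might infer that the study cannot answer the co-medication question at all. That goes too far. All concomitant medicines are recorded (Section 4.3.1), and PPI co-medication is a secondary objective with its own bismuth comparison (Sections 2.2 and 11.7.7).

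What remains is that the text permits the loss, nothing in it protects the sample or the subject's place in the analysis, and the rule runs against the stated purpose.

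**Conclusion.** The concern holds as a conflict within the protocol. Criterion 6, read with Section 4.3.2, permits removal of subjects whose exposure Section 1.2 asks to observe. Before Day 11 the removal can cost the sample. At or after Day 11 it can cost the subject's place in the Per Protocol population. The study may therefore lose part of this exposure, and the result tilts toward no accumulation if any such medicine raises bismuth.

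The size cannot be taken from the documents. At an assumed 10 to 30 users, full retention with no exceedance would give upper limits of 25.9% to 9.5%, which is modest information but more than none. Total loss is the worst case. The expected loss is smaller, because most use that starts during treatment would be found when the sample can still be drawn.

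**What to change.** Reconcile criteria 4 and 6 in Section 4.6, Section 4.3.2, Section 11.6 and Section 11.7.1.2 with Section 1.2. Deleting criterion 6 alone is not enough, because the significant-deviation criterion and the Per Protocol rules could remove the same subjects. The amended text should state that:

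- use of such a medicine is recorded as a concomitant medication, and does not by itself end study participation or exclude the subject from the bismuth analysis;
- the planned Day 11 bismuth and TMB samples are still taken from every subject who has not withdrawn consent;
- bismuth is summarised with and without such medicines, with the group defined from the SmPC interaction section and fixed before database lock.

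Decisions on treatment stay with the treating physician, and no clinical rule is proposed here.

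The cost is a short amendment and one descriptive table. The Day 11 draw is already planned, so no patients, visits or draws are added.
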